### 9.3 HCV RNA Relapse [V]

#### Secondary Outcome Measure (from protocol section 9.2.2.3)

To evaluate virologic evidence of relapse, defined as HCV RNA undetectable (<LLOQ TND) at end-of-treatment but HCV RNA quantifiable ( $\geq$ LLOQ) during followup, will require confirmation and should be performed as soon as possible but within 2 weeks after determination of initial observation.

For analysis purposes, confirmatory values obtained after 2 weeks will be included.

#### Planned Analysis

- a) List: Participants who have virologic evidence of relapse. The listing will include week of HCV RNA undetectable (<LLOQ TND), HCV RNA undetectable at end of study treatment, post treatment week of HCV RNA detectable ( $\geq$ LLOQ) and confirmation of HCV RNA detectability (HCVRNALDMS)

### 9.4 SOF or LDV-associated resistance mutations

#### Secondary Outcome Measure (from protocol section 9.2.2.4)

Development of SOF or LDV-associated resistance mutations. The set of mutations to be considered will be defined at the time of analysis based on information from other studies available at that time.

#### Planned Analysis

- a) The analysis will be performed outside of SDAC. The raw data will be downloaded to the final database using the GETBSS HCV script.

### 9.5 AEs by type of event [V]

#### Secondary Outcome Measure (from protocol section 9.2.2.5)

Occurrence of the AEs detailed in section 9.2.1.2 of the protocol (Section 9.1 in this document) by type of event. Type of events include: diagnosis, sign, symptom, laboratory abnormality, SAE according to ICH criteria, or treatment-limiting AE. Additional analysis of selected renal safety parameters is included because of a concern that participants taking TDF might be at increased risk for such events.

#### Planned Analysis

- a) Table: list of events (EVW0206, EVW0207), including HIV ARV regimen.
- b) Table: summarizing creatinine clearance and urinalysis during on study treatment by participants who were taking TDF in combination either with a boosted PI or with COBI and participants taking other HIV ARV regimens.
- c) Figure: Individual participant plots of creatinine clearance over time distinguishing participants who took TDF with a boosted PI, from participants who took TDF with COBI, from other participants.

- d) Table of protein urinalysis results at each scheduled measurement week distinguishing participants taking TDF with either a boosted PI or COBI from other participants: Number (%) in each protein category.

## **9.6 Change in HIV-1 RNA [V]**

### Secondary Outcome Measure (from protocol section 9.2.2.6)

Change in HIV-1 RNA from last measurement prior to start of study treatment to each subsequent scheduled HIV-1 RNA measurement time: for participants on ART at study entry, these will be categorized as changes from <50 copies/mL to ≥50 copies/mL, or vice versa; for participants not on ART at study entry, quantitative change in log10 HIV-1 RNA will be considered. Windows for measurements to be included and the algorithm for selecting measurements within each window will be as described for HCV RNA measurements above.

### Planned Analysis

Each analysis will be done by ARV use at study entry (yes vs no) (RNALDMS, HXW0171)

- a) Table: summarize HIV-1 RNA measurements at each time point
- b) Table: summarize HIV-1 RNA changes from last measurement prior to study treatment to each subsequent HIV-1 RNA measurement
- c) Figure: summarize HIV-1 RNA measurements at each time point
  - i. For participants on ARVs at study entry: the figure will summarize the proportion of participants who had HIV-1 RNA < 50 copies/mL with 95% confidence interval around the proportion
  - ii. For participants not on ARVs at study entry: the figure will summarize the HIV-1 RNA median and IQR (Q1, Q3)
- d) Figure: summarize HIV-1 RNA changes at each time point
  - i. For participants on ARVs at study entry: the figure will summarize the proportion of participants who had HIV-1 RNA < 50 copies/mL with 95% confidence interval around the proportion
  - ii. For participants not on ARVs at study entry: the figure will summarize the HIV-1 RNA median and IQR (Q1, Q3)

## **9.7 Change in CD4+ cell count and CD4+ cell percentage [V]**

### Secondary Outcome Measure (from protocol section 9.2.2.7)

Change in CD4+ cell count from last measurement prior to start of study treatment to each subsequent scheduled CD4+ cell count measurement time. Windows for measurements to be included and the algorithm for selecting measurements within each window will be as described for HCV RNA measurements above.

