## 1 Introduction

This document describes the content proposed for the primary statistical analysis of ACTG A5327. The focus of this analysis will address the primary safety and efficacy objectives for Cohort 2 (8 weeks of treatment) as well as the secondary objectives for which data will be available at the time of the primary analysis. Details about analyses for review by the Study Monitoring Committee (SMC) are not included in this SAP as all participants had completed study treatment by the time of preparation of this SAP and no further reviews of the study by the SMC were to be undertaken.

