Note: Baseline is defined as the closest value on/before date of start of study treatment.

- ii. Baseline CD4+ cell count (/mm^3) (LBW0054): N, median, 1st and 3rd quartile, minimum and maximum;  
Note: Baseline is defined as the arithmetic mean of screening and entry values or, in the absence of one value, the one available.
  - iii. Baseline CD4+ cell percent (LBW0054): N, median, 1st and 3rd quartile, minimum and maximum;  
Note: Baseline is defined as the arithmetic mean of screening and entry values or, in the absence of one value, the one available.
- d) Table summarizing HIV-1 antiretroviral therapy (ARVs)
- i. Receiving HIV ARVs prior to entry (ANSTAB): number (%) yes and no
  - ii. HIV ARV regimen at entry (TXT0004): number (%) on each regimen
  - iii. HIV ARV regimen of interest for renal functions (TXT0004): number (%) on TDF + boosted PI, COBI, and other ARV regimens
  - iv. NNRTIs (TXT0004): number (%) on efavirenz, rilpivirine, tenfovir, and abacavir based regimens
  - v. Integrase Inhibitors (IIs) (TXT0004): number (%) on raltegravir and dolutegravir based regimens
  - vi. Protease Inhibitors (PIs) (TXT0004): number (%) on boosted PI based regimens
- e) Table summarizing baseline laboratory evaluations
- For each laboratory evaluation the following will be presented unless otherwise specified: N, median, 1st and 3rd quartile, minimum and maximum. If the lab value is graded, DAIDS grading scale will also be presented.
- Note: Baseline is defined as the last available value on or before the date of starting study treatment. Fasting per protocol is defined as nothing to eat or drink except prescription medications and water for at least 8 hours prior to the procedure. If nonfasting at the screening visit, the participant should return within 7 days for fasting blood draw. These panels are performed at the designated testing laboratory; see A5237 lab processing chart [LPC] for directions.
- i. Hematology characteristics (F2850): hematocrit, hemoglobin (g/dL), platelets (cells/mm^3), red blood cell (RBC) count, white blood cell (RBC) count (cells/mm^3), WBC differentials (absolute and percentage: lymphocytes, monocytes, neutrophils, eosinophils, basophils, reticulocyte count) and mean corpuscular volume (MCV).

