### Planned Analysis

- a) Table: summarize CD4+ cell count and percentage measurements at each time point (LBW0054: N, median, 1st and 3rd quartile, minimum and maximum)

- b) Table: summarize CD4+ cell count and percent changes from the last measurement prior to study treatment to each subsequent CD4+ cell count measurement (LBW0054: N, median, 1st and 3rd quartile, minimum and maximum)
- c) Figure: summarize CD4+ cell count and percentage median and IQR (Q1, Q3)
- d) Figure: summarize CD4+ cell count and percent change median and IQR (Q1, Q3)

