## 10 Analysis datasets

Preliminary list of analysis datasets [V]

**baseline [V]** – key baseline variables used in multiple summaries

**studystatus [V]** – study status information, e.g. on study, off study, reason off study

**screeninfo [V]** – screening failures

**hivrna [V]** – longitudinal HIV-1 RNA with calculated study weeks

**cd4 [V]** – longitudinal CD4 cell count with calculated study weeks

**arv2 [V]** – HIV-1 antiretrovirals at entry and during study

**hcvrxadhere [V]** – adherence to study drugs with calculated study weeks

**primsafe[IP]** – primary safety events with calculated weeks on treatment

**hcvrna[IP]** – primary efficacy analysis with longitudinal HCV RNA with calculated study weeks

NOTE: Other datasets that are created will be added in a later version of this document.

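### Must change in CD4+ be measured from the same averaged baseline that Section 5 uses to describe the participants?

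*SAP*

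**What the plan says.** Section 5, in the table of HIV disease status, states for CD4+ count and again for CD4+ percent: "Baseline is defined as the arithmetic mean of screening and entry values or, in the absence of one value, the one available".

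Section 9.7, whose outcome definition is attributed to protocol section 9.2.2.7, takes change in count from the single last value before treatment: "Change in CD4+ cell count from last measurement prior to start of study treatment to each subsequent scheduled CD4+ cell count measurement time". Planned table b) applies the same reference to both measures: "summarize CD4+ cell count and percent changes from the last measurement prior to study treatment to each subsequent CD4+ cell count measurement". The remaining CD4+ outputs are a table of values by time point and two figures of medians and quartiles. The tables give N, median, quartiles, minimum and maximum.

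Section 10 lists a baseline dataset, described as "key baseline variables used in multiple summaries", and a separate longitudinal CD4+ dataset. It does not say which pre-treatment CD4+ value each one holds. No sentence in the SAP links the two definitions.

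**The concern.** A reader who sees a baseline CD4+ in one table and a change from pre-treatment in another will expect the second to start from the first. Here it does not. A participant with two differing pre-treatment values has an averaged value in Section 5 and a change in Section 9.7 that starts from the later value alone.

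It also looks unintended. For HIV-1 RNA, the Section 5 baseline and the Section 9.6 reference are in substance the same value. CD4+ alone gets an averaged baseline that is then not used for change. Averaging two readings is a usual way to damp visit-to-visit noise, so Section 9.7 seems to discard information already collected. At stake would be the coherence of a listed secondary outcome, and perhaps some precision.

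**Working it through.** The SAP states no figure on this point, so there is nothing to reproduce. The check is algebra, with an assumed within-person SD.

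**Set-up.** Let S be the screening value, E the entry value (taken as the last before treatment) and F a follow-up value:

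- S = m + e1
- E = m + d + e2
- F = m + d + c + e3

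Here d is any true shift between screening and entry, c is the true change after entry, and the errors have variance s². Between participants, c has variance t² and d has variance δ².

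**Size of the mismatch.** Change under Section 9.7 is F − E. Change from the Section 5 baseline is F − (S + E)/2. The second minus the first is (E − S)/2.

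- Assumed S = 500, E = 600, F = 650: +50 under 9.7, +100 from the averaged baseline.
- Assumed S = 600, E = 500, F = 650: +150 under 9.7, +100 from the averaged baseline.
- With only one pre-treatment value, or with S = E, the two agree.

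With independent errors and δ² = 0, the SD of (E − S)/2 is s√2/2 = 0.71s. For assumed s of 50, 100 and 150 cells/mm3 this is 35, 71 and 106 cells/mm3. If there is no systematic shift, the gap averages zero, so neither reference biases the group mean change.

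**What each reference measures.** Leaving errors aside, F − E = c, while F − (S + E)/2 = c + d/2. If CD4+ truly moves between screening and entry, the averaged reference counts half of that pre-treatment movement as change after entry. The last value does not.

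**Precision.** With independent errors, Var(F − E) = t² + 2s² and Var(F − (S + E)/2) = t² + 1.5s² + δ²/4.

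| Assumption | Reduction from averaging |
|---|---|
| t² = 0, δ² = 0 | 0.5/2 = 25% |
| t² = s², δ² = 0 | 0.5/3 = 16.7% |
| t² = 2s², δ² = 0 | 0.5/4 = 12.5% |
| t² = 0, δ = s | (2 − 1.75)/2 = 12.5% |
| t² = 0, δ = 1.41s | 0% |
| t² = 0, δ = 2s | (2 − 2.5)/2 = −25% |

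Now let the errors follow a first-order autoregression with correlation ρ between adjacent, equally spaced visits, with t² = δ² = 0:

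- Var(F − E) = 2s²(1 − ρ)
- Var(F − (S + E)/2) = s²(1.5 − 0.5ρ − ρ²)
- The difference is s²(1 − ρ)(1 − 2ρ)/2. As a share of the first variance it is (1 − 2ρ)/4.

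That is 25% at ρ = 0, zero at ρ = 0.5, and negative above 0.5.

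**Direction of change.** With zero mean true change and δ² = 0, the two versions differ in sign with probability arccos(r)/π, where r = √[(t² + 1.5s²)/(t² + 2s²)]. For t² = 0, s² and 2s², r is 0.866, 0.913 and 0.935, giving 16.7%, 13.4% and 11.5%. At t² = 0 every observed change is noise, so its sign carries no information under either reference. Section 9.7 has no increase-or-decrease outcome in any case.

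**What the report will show.** Section 9.7 plans no participant-level CD4+ listing or plot. Medians are not additive: with one common reference, the median change would still generally differ from median follow-up minus median baseline. Harmonising the references would not make the published tables reconcile.

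**The case for a change.** The strongest case for a change is that the two definitions are both current, differ for count and for percent, and are left unexplained. A programmer drawing on the shared baseline dataset could merge the averaged value into the change calculation. Table a) and figure c) in Section 9.7 do not say which pre-treatment value they show. Measuring change from the Section 5 baseline, with the protocol version kept as a sensitivity summary, would need one sentence, some footnotes and no new data.

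The textual mismatch stands. The rest carries less weight. Section 9.7 names its reference in the outcome definition and again in table b), so using the averaged value would be a programming error that the text already excludes, and the section is flagged for program validation. Section 5 sets its reference value item by item: entry for HCV RNA, closest on or before treatment start for HIV-1 RNA, an average for CD4+, last available for laboratory tests. An averaged CD4+ for describing the population fits that practice. The unlabelled pre-treatment point in table a) and figure c) is a gap that a table footnote settles when the report is produced.

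The proposed remedy also has a price. It would demote a definition attributed to the protocol at a stage when "all participants had completed study treatment by the time of preparation of this SAP". It would also break the parallel with Section 9.6, where change in HIV-1 RNA uses the last pre-treatment value.

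**Conclusion.** No change is needed. The two CD4+ references serve different purposes: one describes the participants at entry, the other anchors a change outcome. Each is defensible and can be programmed as written. They differ by (E − S)/2, and only for participants with two differing pre-treatment values. The SD of that gap is 0.71s under independent errors and no true shift, or 35 to 106 cells/mm3 for an assumed s of 50 to 150. The possible precision gain from averaging runs from 25% through zero to a loss, depending on error correlation and pre-treatment shift, and the SAP gives no information on either. That is a fair trade-off, and it does not justify replacing a protocol-attributed reference after treatment was complete. Naming the reference under each CD4+ table and figure is good reporting practice but alters no result. The outcome is descriptive and secondary, and the primary efficacy and safety analyses are untouched.

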### Planned Analysis

- a) Table: summarize CD4+ cell count and percentage measurements at each time point (LBW0054: N, median, 1st and 3rd quartile, minimum and maximum)

- b) Table: summarize CD4+ cell count and percent changes from the last measurement prior to study treatment to each subsequent CD4+ cell count measurement (LBW0054: N, median, 1st and 3rd quartile, minimum and maximum)
- c) Figure: summarize CD4+ cell count and percentage median and IQR (Q1, Q3)
- d) Figure: summarize CD4+ cell count and percent change median and IQR (Q1, Q3)

## 9.8 Adherence [V]

### Secondary Outcome Measure (from protocol section 9.2.2.8)

Measures of adherence: for each LDV/SOF at each visit: (a) self-reported adherence as measured by whether or not a participant reports having taken all doses; and (b) proportion of doses taken since the previous visit as determined by pill count.

### Planned Analysis

- a) Table: summarize proportion of participants taking all doses of medication within the 3 days prior to the evaluation (QL0757)
- b) Table: summarize the number (%) of doses taken since the previous visit, along with descriptive statistics (N, median, 1st and 3rd quartile, minimum and maximum) (EVW0320)

## 9.9 Immune Parameters

### Secondary Outcome Measure (from protocol section 9.2.2.9)

Immune parameters: changes in magnitude of induction of ISGs by Nanostring, changes in IP-10 levels, and changes in T cell function (CD4+ proliferative and CD8 CTL assays) at end of treatment and end of followup compared to study entry. Analysis will be performed as a function of IL28B genotype.

### Planned Analysis

The analysis plan may be updated with additional analysis for this secondary outcome. Immune parameter tables are TBD.

- a) Table: summarize ISGs at each time point and change in ISG from baseline
- b) Table: summarize IP-10 levels at each time point and change in IP-10 from baseline
- c) Table: summarize T cell function at each time point and change in T cell function from baseline

## 9.10 Pharmacology Analysis

A separate Statistical Analysis Plan will be developed for the Pharmacology objectives.

## 10 Analysis datasets

Preliminary list of analysis datasets [V]

**baseline [V]** – key baseline variables used in multiple summaries

**studystatus [V]** – study status information, e.g. on study, off study, reason off study

**screeninfo [V]** – screening failures

**hivrna [V]** – longitudinal HIV-1 RNA with calculated study weeks

**cd4 [V]** – longitudinal CD4 cell count with calculated study weeks

**arv2 [V]** – HIV-1 antiretrovirals at entry and during study

**hcvrxadhere [V]** – adherence to study drugs with calculated study weeks

**primsafe[IP]** – primary safety events with calculated weeks on treatment

**hcvrna[IP]** – primary efficacy analysis with longitudinal HCV RNA with calculated study weeks

NOTE: Other datasets that are created will be added in a later version of this document.
